## Clinical Investigation Plan

assumes that the effectiveness endpoint definition includes effectiveness failure for any documented (symptomatic or asymptomatic) AF/AFL/AT episode of >30 seconds in duration.

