- If the subject has a continuous atrial arrhythmia throughout a 12-lead ECG recording after the blanking period indicating AF/AFL/AT recurrence, this will be considered sufficient documentation of recurrence unless there is evidence that the recorded arrhythmia is short-lived and less than 30 seconds as determined by the investigator, or
- Any ablation in the left atrium using an ablation catheter other than TactiFlex SE.

Cavotricuspid isthmus (CTI)-dependent AFL that occurs alone either during or after the blanking period will be considered an exception to being considered a recurrence, as CTI-dependent AFL is easily treated with cavotricuspid isthmus ablation and is not an iatrogenic arrhythmia following a left atrial ablation procedure for AF. Occurrence of CTI-dependent AFL confirmed by entrainment maneuvers that occurs at any time during the follow-up period and is ablated, will not be considered a primary effectiveness endpoint failure.

The performance goal (PG) is set at 50% based on the chronic acceptable success rate for paroxysmal AF at 12-months in the 2017 Consensus Statement [17]. The 50% chronic acceptable success rate

---

 For subjects that have a repeat ablation procedure ≤80 days after the initial procedure, only failure to achieve acute procedural success during the repeat procedure will contribute to primary effectiveness endpoint.

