- If the subject requires a second repeat AF ablation procedure ≤ 80 days after the initial procedure, or
- Any use of a new class I or III AAD for AF after the blanking period, or
- Any use of a class I or III ADD for AF at a dose higher than that previously failed by the patient, or
- If the subject requires a cardioversion (electrical or pharmacological) for the treatment of AF after the blanking period, or
- If the subject has a continuous atrial arrhythmia throughout a 12-lead ECG recording after the blanking period indicating AF/AFL/AT recurrence, this will be considered sufficient documentation of recurrence unless there is evidence that the recorded arrhythmia is short-lived and less than 30 seconds as determined by the investigator, or
- Any ablation in the left atrium using an ablation catheter other than TactiFlex SE.

¹ For subjects that have a repeat ablation procedure ≤ 80 days after the initial procedure, only failure to achieve acute procedural success during the repeat procedure will contribute to primary effectiveness endpoint.

Statistical Analysis Plan

Cavotricuspid isthmus (CTI)-dependent AFL that occurs alone either during or after the blanking period will be considered an exception to being considered a recurrence, as CTI-dependent AFL is easily treated with cavotricuspid isthmus ablation and is not an iatrogenic arrhythmia following a left atrial ablation procedure for AF. Occurrence of CTI-dependent AFL confirmed by entrainment maneuvers that occurs at any time during the follow-up period and is ablated, will not be considered a primary effectiveness endpoint failure.

Counting the use of new or higher than previously failed doses of AADs after the blanking period as effectiveness failures is consistent with the primary effectiveness endpoint recommendations in the FDA Guidance on Clinical Study Designs for Percutaneous Catheter Ablation for the Treatment of Atrial Fibrillation [14].

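### The 50% effectiveness goal is stated to assume that any AF/AFL/AT episode is a failure, yet the endpoint exempts isolated CTI-dependent flutter; the two are not reconciled

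*Protocol*

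**What the plan says.** Protocol section 4.1.2 gives the goal and its source: "The performance goal (PG) is set at 50% based on the chronic acceptable success rate for paroxysmal AF at 12-months" in the cited consensus statement. It then gives the condition attached to that rate, namely that it "assumes that the effectiveness endpoint definition includes effectiveness failure for any documented (symptomatic or asymptomatic) AF/AFL/AT episode of >30 seconds in duration".

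The paragraph before the goal reads: "Cavotricuspid isthmus (CTI)-dependent AFL that occurs alone either during or after the blanking period will be considered an exception to being considered a recurrence". A second sentence in that paragraph is narrower. It says that "Occurrence of CTI-dependent AFL confirmed by entrainment maneuvers that occurs at any time during the follow-up period and is ablated" does not count as a primary effectiveness failure. SAP section 1.4.1.2 repeats both sentences, including that such flutter "will be considered an exception to being considered a recurrence".

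Protocol section 4.1.2.1 names two things taken from the consensus statement: the 30-second AF/AFL/AT definition and the 50% rate. The flutter exemption is not among them.

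Two further passages bear on which events are exempt. The failure list in section 4.1.2 counts a repeat procedure after day 80 when it is for AF. Section 6.6.4 counts a repeat procedure after day 80 for AF, AFL or AT recurrence, with no carve-out for CTI-dependent flutter.

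**The concern.** This is a single-arm trial. Primary effectiveness is judged only by comparing the observed rate with 50%, and trial success requires rejecting both primary null hypotheses (Protocol section 8.11). That comparison is easiest to defend when the endpoint counts the same events as the benchmark. An isolated CTI-dependent flutter lasting more than 30 seconds after blanking is a documented AFL episode. It is a failure under the condition stated for the 50% and not a failure under the endpoint. The three powered secondary endpoints take over the primary definition with one change each (Protocol section 4.2), so they carry the same exemption.

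The scope of the exemption is also unsettled. Under its first sentence, any CTI-dependent flutter occurring alone is exempt. If the second sentence sets the conditions, a flutter seen only on ECG, TTM or Holter, never studied by entrainment and never ablated, would count as a failure. The same subject could be classified either way.

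**Working it through.** **Textual comparison**

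- Condition stated for the goal (Protocol 4.1.2): any documented AF/AFL/AT episode of more than 30 seconds is a failure. No exception is mentioned.
- Endpoint (Protocol 4.1.2, SAP 1.4.1.2): the same, minus CTI-dependent AFL occurring alone.
- Criteria attributed to the source (Protocol 4.1.2.1): the 30-second definition and the 50%. The exemption is not listed.
- Reconciliation: none in the visible text. SAP Appendix E, the effectiveness rationale, is redacted, so nothing is inferred from its absence.

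**Can the plan's own figures be reproduced?** No. The 50% is a cited benchmark, and alpha, power, assumed rate and attrition are redacted. What follows is an illustration only.

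**Inputs.** N = 305 (main study, Protocol 5.6); p0 = 0.50 (Protocol 4.1.2); one-sided alpha of 0.025 or 0.05 (assumed); either no attrition or 10% attrition, 0.9 × 305 = 274.5, taken as 274 (assumed). An exact binomial test stands in for the planned Kaplan-Meier analysis. Let x be the percentage points that the exemption adds to the success rate, that is, the share of subjects whose only failing event is exempted flutter. The documents give no value for x. One point of 305 is 3.05 subjects.

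**Pass mark.** The smallest r with P(X ≥ r | N, 0.50) ≤ alpha. For N = 305 and alpha = 0.025, r = 171, or 171/305 = 56.1%, with exact level 0.0195.

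**Chance of passing when the true rate with all flutter counted is 50%.** This is P(X ≥ r | N, 0.50 + x/100):

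| x (points) | N=305, 2.5% (r=171) | N=305, 5% (r=168) | N=274, 2.5% (r=154) |
|---|---|---|---|
| 0 | 0.0195 | 0.0428 | 0.0230 |
| 1 | 0.0433 | 0.0854 | 0.0480 |
| 2 | 0.0861 | 0.1538 | 0.0912 |
| 3 | 0.1550 | 0.2513 | 0.1581 |

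In the first column, 1 to 2 points (about 3 to 6 subjects) multiply the chance of passing by 0.0433/0.0195 = 2.2 and 0.0861/0.0195 = 4.4.

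**When it does not matter.** With r = 171 and x = 2, if the true rate under the endpoint is 65%, the chance of passing is 0.9995 with the exemption and 0.9945 with all flutter counted (63%). If it is 58%, the figures are 0.7715 and 0.5147 (56%). The exemption could decide the result only when the true rate is near the pass mark.

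**The case against.** A reader might infer that the measured rate is not like-for-like with its goal and that the primary test is therefore easier to pass. The documents do not support that.

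- Whether the source of the 50% applies the same flutter exemption is not stated. If it does, the comparison is sound and only the sentence about the 50% is loosely worded.
- The endpoint also counts failures that this sentence does not mention: acute procedural failure, a new or higher-dose Class I or III AAD, cardioversion after blanking, late repeat AF ablation without a documented episode, and left-atrial ablation with another catheter. These lower the rate, so the net direction against the goal is open.
- Exempted events may be few. The flutter must occur alone, the second exemption sentence may narrow it further, and Protocol section 6.3.5 requires concomitant ablation for known typical flutter or induced CTI-dependent flutter.
- The sentence about the 50% may be meant to stress that asymptomatic episodes count, which the endpoint respects.
- The exemption is openly disclosed, and SAP section 1.4.3 (item 10) reports freedom from recurrent AFL in subjects treated for typical flutter.

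All of this limits the claim about bias, and it stands. It does not remove the inconsistency. The sentence names AFL and says any episode, the added failure criteria concern other events, and the descriptive item covers only treated subjects and is not set against 50%. A reader might also take the sentence as claiming that the trial's definition already matches the benchmark. It says only what the 50% assumes.

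**Conclusion.** As written, the endpoint does not meet the condition that the Protocol attaches to its own goal, and no visible text reconciles the two. The exemption on its own can only raise the success rate. Nothing in the documents fixes by how much, or shows that the net comparison with 50% is favourable.

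The figures rest on an assumed alpha, a binomial stand-in for Kaplan-Meier, and a true all-flutter rate of exactly 50%. Under those assumptions, an added 1 to 2 points take the chance of passing from 0.0195 to between 0.043 and 0.086. With a true rate well above 56.1% the conclusion would not change. This is a case for clarification and one inexpensive supportive analysis. It does not show that the primary analysis is invalid.

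**What to change.** 1. Pre-specify in the SAP (section 2.3.1.2 or 2.13) a supportive analysis in which every AF/AFL/AT episode of more than 30 seconds after blanking, CTI-dependent flutter included, is a failure, and report it against 50%. The exemption can stay in the primary analysis. The supportive version needs no judgement about the flutter mechanism.
2. State in Protocol section 4.1.2 whether the 50% benchmark carries the CTI exception. If it does, add the exception to the sentence describing what the rate assumes. If it does not, or this is unknown, say that the primary endpoint departs from the benchmark in this respect.
3. Reconcile the two exemption sentences in Protocol section 4.1.2 and SAP section 1.4.1.2, so that it is clear whether any isolated CTI-dependent flutter is exempt or only flutter that is confirmed by entrainment and ablated. Reconcile the failure list in section 4.1.2 with section 6.6.4 on late repeat procedures, so that both classify a late flutter procedure the same way.

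The cost is one extra analysis and some wording. The ECG, TTM and Holter data are already collected and read by the core laboratory (Protocol section 6.7), so neither subject burden nor sample size changes. The supportive rate may be slightly lower than the primary one.

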### 4.1.2.1 Rationale for Selection of the Primary Effectiveness Endpoint

The guideline published by the 2017 Consensus Statement [17] was referred to when defining the primary effectiveness end-point for this clinical investigation. The following criteria were defined from this document for use in this clinical investigation: the definition of detectable AF defined as AF/AFL/AT of at least 30 seconds duration when assessed with ECG monitoring; an acceptable chronic success rate of 50% for PAF.

Counting the use of new or higher than previously failed doses of AADs after the blanking period as effectiveness failures is consistent with the primary effectiveness endpoint recommendations in the FDA Guidance on Clinical Study Designs for Percutaneous Catheter Ablation for the Treatment of Atrial Fibrillation [32].

## 4.2 Powered Secondary Endpoints

Type I error among secondary endpoints will be controlled using appropriate statistical methodology as outlined in the Statistical Analysis Plan.

### 4.2.1 AAD-Free Secondary Effectiveness Endpoint

The AAD-Free Secondary Effectiveness Endpoint has the same definition as the Primary Effectiveness Endpoint, except that any use of Class I or III AADs after the 90-day blanking period will count as a therapy failure in this analysis.

### 4.2.2 Single-Procedure Secondary Effectiveness Endpoint

The Single-Procedure Secondary Effectiveness Endpoint has the same definition as the Primary Effectiveness Endpoint, except that any repeat ablation in the left atrium will count as a failure.

### 4.2.3 Symptomatic Secondary Effectiveness Endpoint

The Symptomatic Secondary Effectiveness Endpoint has the same definition as the Primary Effectiveness Endpoint, except that episodes of documented recurrence without documented evidence of symptoms after the 90-day blanking period will not count as a therapy failure in this analysis.

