### **12-Month (365 ± 30 days) Follow-Up Visit**

The 12-month follow-up visit is a scheduled in-person site visit.

- 12-lead ECG
- Document AAD and anticoagulant usage
- Administer the AFEQT and EQ-5D-5L questionnaires
- Document adverse events and protocol deviations
  - If the subject describes symptoms suggestive of pulmonary vein stenosis (e.g. shortness of breath, cough, and hemoptysis), complete CT or MRI imaging of pulmonary veins.
- Administer a 24-hour Holter monitor
- Collect the TTM monitor from the subject

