1.4.2.3 Symptomatic Secondary Effectiveness Endpoint

The Symptomatic Secondary Effectiveness Endpoint has the same definition as the Primary Effectiveness Endpoint, except that episodes of documented recurrence without documented evidence of symptoms after the 90-day blanking period will not count as a therapy failure in this analysis.

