2.3.2.3 Symptomatic Secondary Effectiveness Endpoint

The Symptomatic Secondary Effectiveness Endpoint has the same definition as the Primary Effectiveness endpoint, except that documented recurrence without documented evidence of symptoms after the 90-day blanking period will not count as a therapy failure in this analysis.

The hypothesis is stated as follows:

$$H_0: P \leq [REDACTED]$$

$$H_a: P > [REDACTED]$$

where P is the percentage of subjects free from any primary effectiveness endpoint event other than asymptomatic recurrence after the 90-day blanking period, and [REDACTED] is the performance goal. [REDACTED]

The analysis population for this secondary endpoint is the primary effectiveness analysis population. The symptomatic secondary effectiveness endpoint rate will be calculated using the Kaplan-Meier method based on the primary effectiveness analysis population. [REDACTED]

Statistical Analysis Plan

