2.9 Handling of Missing Data

All analyses will be based on available data with missing data excluded unless otherwise specified in the analysis population for each endpoint.

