2.13 Sensitivity Analyses

In order to assess the impact of missing data on the primary endpoint analysis results, the following sensitivity analyses are planned:

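### The powered symptomatic endpoint excuses any recurrence lacking a symptom record, whereas its tested parameter excuses only asymptomatic recurrence; missing symptom status can therefore bias the rate, and only upward

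*Protocol*

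**What the plan says.** Protocol section 4.2 lists the symptomatic endpoint among the powered secondary endpoints. Section 4.2.3 takes over the primary effectiveness definition with one exception: "episodes of documented recurrence without documented evidence of symptoms after the 90-day blanking period will not count as a therapy failure in this analysis". SAP section 1.4.2.3 has the same rule, under which a recurrence "without documented evidence of symptoms after the 90-day blanking period will not count as a therapy failure".

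SAP section 2.3.2.3 restates the rule and then sets up the hypothesis. There P is the percentage of subjects "free from any primary effectiveness endpoint event other than asymptomatic recurrence after the 90-day blanking period", tested one-sided (H0: P at or below the performance goal). On the estimator it says: "The symptomatic secondary effectiveness endpoint rate will be calculated using the Kaplan-Meier method based on the primary effectiveness analysis population".

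On missing data, SAP section 2.9 says: "All analyses will be based on available data with missing data excluded unless otherwise specified in the analysis population for each endpoint". The sensitivity analyses in SAP section 2.13 are introduced with: "In order to assess the impact of missing data on the primary endpoint analysis results, the following sensitivity analyses are planned". Protocol section 8.8 likewise names only the primary safety and primary effectiveness endpoints.

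**The concern.** A recurrence without evidence of symptoms is not the same thing as a recurrence without symptoms. The endpoint definition treats an unknown symptom status as if it were a confirmed absence of symptoms. P, as written, does not. What would be counted can therefore differ from what is tested.

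The direction matters because this is a single-arm comparison with a performance goal. No control arm shares the documentation gap, so weaker symptom recording can only help to reject the null hypothesis. The general rule of excluding missing data offers no protection, because the definition turns the missing record into a non-event before that rule could apply.

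**Working it through.** **No figure to reproduce.** The performance goal, assumed rate, alpha and sample size for this endpoint are redacted or not visible (Protocol section 8.3.5; SAP sections 2.3.2.3 and 2.4.5 and Appendix H).

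**1. The two rules side by side, for a post-blanking recurrence that is the subject's only failure.**

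| Symptom record | True state | Endpoint definition | Parameter P |
|---|---|---|---|
| Symptoms recorded | symptomatic | failure | failure |
| Absence recorded | asymptomatic | exempt | exempt |
| None | symptomatic | exempt | failure |
| None | asymptomatic | exempt | exempt |

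Only the third row differs, and it differs in one direction. In the Kaplan-Meier estimate such a subject stays in the risk set without an event. One downward step disappears and no later factor gets smaller, so the 12-month rate rises.

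**2. Where a record could be missing.** Scheduled transtelephonic monitoring (TTM) runs in 14-day periods between the 3- and 12-month visits: (365 - 91)/14 = 19.6, so about 19 full periods. There are 12-lead ECGs at 3 and 12 months, and the 12-month list says "Administer a 24-hour Holter monitor". Neither these visit lists nor Table 4 shows a symptom query or diary tied to the recordings. Protocol section 6.7 gives the core laboratory the task of adjudicating arrhythmias and does not mention symptoms. The one visible link is the TTM transmission that a subject sends during a symptomatic episode.

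**3. Size, as an illustration.** Bias = r x s x m, where

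- r = share of subjects whose only failure is a documented recurrence,
- s = share of those who were truly symptomatic,
- m = share of those with no symptom record.

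All three values are assumptions. N = 305 is main-study enrolment (Protocol section 5.6); the analysis population itself is redacted.

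| r | s | m | Bias (points) | Subjects of 305 |
|---|---|---|---|---|
| 10% | 30% | 10% | 0.3 | 0.9 |
| 20% | 60% | 25% | 3.0 | 9.2 |
| 30% | 90% | 50% | 13.5 | 41.2 |
| any | any | 0 | 0 | 0 |

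**4. What such a bias would do to the test.** Further assumptions: one-sided alpha 0.025, goals of 50%, 60% and 70%, true P equal to the goal, and an exact binomial test with N = 305 in place of Kaplan-Meier. The smallest success counts that reject are 171, 201 and 230. The probability of a false success is:

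| Upward bias | Goal 50% | Goal 60% | Goal 70% |
|---|---|---|---|
| 0 points | 0.020 | 0.020 | 0.021 |
| 1 point | 0.043 | 0.044 | 0.049 |
| 2.5 points | 0.117 | 0.121 | 0.141 |
| 5 points | 0.376 | 0.396 | 0.465 |

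**The case against.** A reader might infer that the success rate is overstated. The documents do not show that. It would require symptomatic recurrences that went unrecorded, and no section gives their number. With complete records the bias is zero.

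A reader might also infer that missing symptom status makes a subject a success. That is too broad. The exemption touches only the documented-recurrence component. Protocol section 4.1.2 still fails a subject for cardioversion for AF after blanking, late repeat ablation for AF, a new or higher-dose Class I or III drug, lack of acute procedural success, or left atrial ablation with another catheter. A later recurrence with recorded symptoms also counts.

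Nor can it be said that the forms lack a symptom field or that the SAP lacks a rule for unknowns. The case report forms are supplied separately, and Appendix H and part of SAP section 2.3.2.3 are redacted. Staff contact around scheduled TTM transmissions is planned (required in Protocol section 3.2, recommended in section 6.6.3, in both places as local rules permit), and it could elicit symptoms, although the text does not call for the question.

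The wording of P may be shorthand for the fuller rule stated just before it. That is a fair reading, but it settles the mismatch in favour of the rule that excuses unknowns, so the upward direction remains. Finally, the stakes are limited: under Protocol section 8.11 trial success rests on the two primary endpoints, and the primary effectiveness endpoint counts recurrences with or without symptoms.

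**Conclusion.** The point holds as a defect of definition. The counting rule and the tested parameter diverge when a symptomatic recurrence has no symptom record. For subjects whose only failure is that recurrence, the divergence can raise the estimate and cannot lower it. The stated missing-data sensitivity analyses do not name this endpoint.

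The size cannot be derived from the documents. The 3-point example and the range of 0.3 to 13.5 points rest wholly on assumed shares. They are not bounds, and the value is 0 if records are complete. Under the assumptions in step 4, even 1 point would roughly double the false-success probability, from about 0.02 to between 0.04 and 0.05. The change should be made because a powered, hypothesis-tested endpoint is affected, but it does not bear on the primary conclusions.

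**What to change.** - **Definition.** In Protocol section 4.2.3 (and the summary in Appendix X) and SAP sections 1.4.2.3 and 2.3.2.3, align the definition with P, so that the exemption applies to recurrences recorded as asymptomatic. State what counts as symptom documentation for each type of recording.
- **Capture.** Record symptom status as yes, no or unknown, prospectively, for each recurrence found on TTM, ECG or Holter, if the forms do not already do so. It cannot be reliably reconstructed later.
- **Reporting.** Give the number of recurrences of unknown status and pre-specify a sensitivity analysis of this endpoint that counts them as failures.

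How unknowns enter the main analysis is open to debate. Counting them as failures could bias the rate downward, and the basis of the performance goal is redacted, so comparability with it cannot be checked. The SAP should state one rule and show the result under the other.

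The cost is a sentence in each document, a form field for each recording type where it is missing, and one extra analysis. The reported rate may become slightly less favourable.
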